### **7.2.2 Exclusion criteria related to the current knowledge of Sanofi compound**

- E 11. Pregnant or breastfeeding woman
- E 12. Women of childbearing potential not protected by highly-effective contraceptive method(s) of birth control (as defined in the informed consent form and/or in a local protocol addendum/amendment) over the study period and for at least 3 months following the last dose of sarilumab, and/or who are unwilling or unable to be tested for pregnancy
- E 13. History of severe allergic or anaphylactic reactions to human, humanized, or murine monoclonal antibodies (or to any of the excipients associated to sarilumab)
- E 14. Immunization with a live/attenuated vaccine within 4 weeks prior to Baseline
- E 15. Stage III or IV cardiac failure according to the New York Heart Association classification
- E 16. History of previous gastrointestinal perforation or diverticulitis
- E 17. Known active current/ recurrent infections (including but not limited to active tuberculosis [TB] or history of incompletely treated TB and atypical mycobacterial disease, hepatitis B and C, and herpes zoster)  
  
NOTE: in case of latent TB infection the patient may be included if a subsequent appropriate anti TB treatment is initiated since at least 3 weeks
- E 18. Positive hepatitis B surface antigen (HbsAg), and/or positive total hepatitis B core antibody, and/or positive hepatitis C antibody (HCV) at the Screening visit
- E 19. Evidence of serious uncontrolled concomitant disease, including severe uncontrolled hypercholesterolemia or hypertriglyceridemia
- E 20. Patients with any of the following laboratory abnormalities at the Screening or Baseline visit:

- Hemoglobin <8.5 g/dL
- White blood cells <3000/mm^3
- Absolute neutrophil count <2000/mm^3
- Absolute lymphocyte count <500/mm^3
- Platelet count <150 000 cells/mm^3
- Creatinine clearance <30 mL/min
- AST or ALT >1.5 x ULN.
- Bilirubin (total) >ULN, unless Gilbert's disease has been determined by genetic testing and has been documented
- Total fasting cholesterol >3.50 g/L [9.1 mmol/L]) or triglycerides >5.00 g/L [5.6 mmol/L])

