### **9.2.2.2 Laboratory safety variables**

The clinical laboratory data consist of blood analysis (including hematology, serum chemistry, and urinalysis). Clinical laboratory values will be analyzed after conversion into standard international units. International units will be used in all listings and tables.

The following laboratory analyses will be performed locally, according to the Schedule of Assessment (see Section 1.2):

- Hematology: hemoglobin, platelet count, and complete blood count (CBC)
- Serum chemistry and liver profile: creatinine clearance, serum iron and 25OHD (at Screening and Week 24 only), alanine aminotransferase (ALT), aspartate aminotransferase (AST), and total bilirubin

- Serum lipids: total fasting cholesterol, triglycerides, high density lipoprotein (HDL) cholesterol, low density lipoprotein (LDL) cholesterol
- Serology: HbsAg, hepatitis B antibody, and hepatitis C virus antibody (at Screening only unless clinically indicated during the trial)
- Pregnancy test: Local pregnancy tests will be conducted for female patients of child-bearing potential. Pregnancy test at Screening will be a serum test. All following pregnancy tests will be urine tests. If a urine test is positive it must be confirmed by a serum pregnancy test
- TB test at Screening (or within the prior 90 days with no abnormality) unless clinically indicated during the trial.

Overnight fasting (>8 hours) prior to blood sampling is required for fasting samples. Patients will only be allowed to drink water during this time. Unscheduled laboratory assessments for safety issues are permitted at any time.

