#### ATP III Classification of LDL, Total, and HDL Cholesterol (mg/dL)

##### LDL Cholesterol – Primary Target of Therapy

<100	Optimal
100-129	Near optimal/above optimal
130-159	Borderline high
160-189	High
≥190	Very high

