$$\text{Value (mmol/L)} = 5.5 \times \text{Value (g/L)}$$

b) Hematology:

$$\text{Value (}\times 10^{12}/\text{L)} = 1000 \times \text{Value (}\times 10^9/\text{L)}$$

$$\text{Value (g/L)} = 0.1 \times \text{Value (g/dL)}$$

(20) **Normal ranges for laboratory tests (hematology)**

	Man	Women	RANGE
Erythrocytes	4,6 à 6,2 millions/mm ³	4,2 -5,4	<4 et >6
Hemoglobin	13.5 – 17 g/dl	12 – 15,5 g/dl	< 12 et > 18
White Blood Cells	3.5 – 10x10 ⁹ /L		<3.5 et > 10x10 ⁹ /L
Neutrophils	3000 – 5800 x10 ⁶ /L		<3000 et >6000 x10 ⁶ /L
Lymphocytes	1500-3000 x10 ⁶ /L		<1500 et >3000 x10 ⁶ /L
Monocytes	300-500 x10 ⁶ /L		<300 et >500 x10 ⁶ /L
Eosinophils	50-250 x10 ⁶ /L		<50 et 250 x10 ⁶ /L
Basophils	15- 50 x10 ⁶ /L		<15 et >50 x10 ⁶ /L
Platelets	150 000 -400 000		<150 000 et > 400 000

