APPENDIX I: GLOBAL ASSESSMENT OF DISEASE ACTIVITY

Patient global assessment of disease activity

[figure not shown]
Considering all the ways that your rheumatoid arthritis affects you, rate how you are doing on the following scale by placing a vertical mark on the line:

Very
0 m

Physician global assessment of disease activity

Place a vertical mark on the line for how you would assess your patient's current activity:

Very
0 m

**APPENDIX J: POTENTIALLY CLINICALLY SIGNIFICANT ABNORMALITIES (PCSA)
CRITERIA**

Parameter	PCSA	Comments
Chemistry Blood		
Creatinine clearance (Cockcroft-Gault equation) (mL/min)	<15 (end stage renal disease) ≥ 15 - < 30 (severe decrease in Glomerular Filtration Rate (GFR))	FDA draft Guidance 2010
	≥ 30 - < 60 (moderate decrease in GFR) ≥ 60 - < 90 (mild decrease in GFR) ≥ 90 (normal GFR)	Pharmacokinetics in patients with impaired renal function-study design, data analysis, and impact on dosing and labeling
Total Bilirubin	> 1.5 ULN > 2 ULN	Must be expressed in ULN, not in μmol/L or mg/L. Concept paper on DILI – FDA draft Guidance Oct 2007. Internal DILI WG Oct 2008. Categories are cumulative. First row is mandatory. Rows following one mentioning zero can be deleted.
AST (SGOT)	By distribution analysis: > 3 ULN > 5 ULN > 10 ULN > 20 ULN	Enzymes activities must be expressed in ULN, not in IU/L. Concept paper on DILI – FDA draft Guidance Oct 2007. Internal DILI WG Oct 2008. Categories are cumulative. First row is mandatory. Rows following one mentioning zero can be deleted.
	Additional analysis: > 1 – 1.5 ULN > 1.5 – 3 ULN > 3 - 5 ULN > 5 – 8 ULN > 8 ULN	
ALT (SGPT)	By distribution analysis: > 3 ULN > 5 ULN > 10 ULN > 20 ULN	Enzymes activities must be expressed in ULN, not in IU/L. Concept paper on DILI – FDA draft Guidance Oct 2007. Internal DILI WG Oct 2008. Categories are cumulative. First row is mandatory. Rows following one mentioning zero can be deleted.
	Additional analysis: > 1 – 1.5 ULN > 1.5 – 3 ULN > 3 - 5 ULN > 5 – 8 ULN > 8 ULN	
ALT (SGPT) and Total Bilirubin	ALT>3 ULN and Total Bilirubin > 2 ULN	Concept paper on DILI – FDA draft Guidance Oct 2007. Internal DILI WG Oct 2008. To be counted within a same treatment phase, whatever the interval between measurement.
Lipid panel		
Total Cholesterol	≥7.74 mmol/L ≥6.2 mmol/L	Threshold for therapeutic intervention.
LDL Cholesterol	≥4.1 mmol/L ≥4.9 mmol/L	Threshold for therapeutic intervention.
	Triglycerides	
Hematology		
Erythrocytes	≥ 6 x10 ¹² /L	

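### The unit conversions in SAP Appendix A (19) are wrong for lipids, hemoglobin and erythrocytes, and as printed would misstate four PCSA rows

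*SAP*

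**What the plan says.** Protocol 9.2.2.2 makes conversion part of the analysis: "Clinical laboratory values will be analyzed after conversion into standard international units. International units will be used in all listings and tables". The formulas are in SAP Appendix A, item (19):

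- Lipid panel, one line for all analytes: "Value (mmol/L)} = 5.5 \times \text{Value (g/L".
- Hematology, count line: "Value (}\times 10^{12}/\text{L)} = 1000 \times \text{Value (}\times 10^9/\text{L".
- Hematology, concentration line: "Value (g/L)} = 0.1 \times \text{Value (g/dL".

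SAP 5.1.4 lists the four lipids in g/L and erythrocytes in ×10⁹/L. Hemoglobin is in g/dL in E 20 and in the normal ranges of Appendix A (20).

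The PCSA limits in SAP Appendix J are in the target units of item (19):

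- total cholesterol: "≥7.74 mmol/L ≥6.2 mmol/L"
- LDL: "≥4.1 mmol/L ≥4.9 mmol/L"
- erythrocytes: at or above 6 ×10¹²/L
- hemoglobin: at or below 115 g/L (men) or 95 g/L (women), at or above 185 or 165 g/L, or a fall of at least 20 g/L from screening

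E 20 (protocol 7.2.2, repeated in SAP 1.3) gives lipid limits in both units: "Total fasting cholesterol >3.50 g/L [9.1 mmol/L]) or triglycerides >5.00 g/L [5.6 mmol/L".

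**The concern.** A single lipid factor cannot serve both cholesterol and triglycerides, and 5.5 matches neither pair in E 20. The two hematology factors have the right size but the wrong direction.

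The percentage of patients with an on-treatment PCSA is a planned safety output (protocol 11.4.3, SAP 5.3.2.4). The protocol also names lipid elevation as an effect of this drug class that will be monitored closely (8.8.2, 10.6). Wrong factors would overstate lipid, low-hemoglobin and erythrocyte abnormalities, and would hide real falls in hemoglobin.

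**Working it through.** **Inputs.** Printed factors: 5.5, 0.1 and 1000 (SAP Appendix A (19)). Paired lipid limits: E 20. Cut-offs in mg/dL: protocol Appendix C, "ATP III Classification of LDL, Total, and HDL Cholesterol (mg/dL". Normal ranges: SAP Appendix A (20). PCSA limits: SAP Appendix J.

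**1. Do the printed factors reproduce the documents' own pairs?** They do not.

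- Cholesterol: 9.1 / 3.50 = 2.60. The SAP factor gives 5.5 × 3.50 = 19.25 mmol/L, not 9.1 (5.5 / 2.6 = 2.1 times too high).
- Triglycerides: 5.6 / 5.00 = 1.12. The SAP factor gives 5.5 × 5.00 = 27.5 mmol/L, not 5.6 (5.5 / 1.12 = 4.9 times too high).
- Nor is 5.5 an inverted factor: 1 / 2.6 = 0.385 and 1 / 1.12 = 0.893.

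**2. Cross-check of 2.6 against Appendix J.** The ATP III cut-offs of 240 mg/dL (total cholesterol) and 160 and 190 mg/dL (LDL) are 2.40, 1.60 and 1.90 g/L.

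| Cut-off (g/L) | × 2.6 | × 5.5 | Appendix J limit (mmol/L) |
|---|---|---|---|
| Total 2.40 | 6.24 | 13.20 | 6.2 |
| LDL 1.60 | 4.16 | 8.80 | 4.1 |
| LDL 1.90 | 4.94 | 10.45 | 4.9 |

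**3. Level in g/L at which each lipid limit would trigger** (limit divided by factor).

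| Limit (mmol/L) | With 5.5 | With 2.6 |
|---|---|---|
| Total 6.2 | 1.13 | 2.38 |
| Total 7.74 | 1.41 | 2.98 |
| LDL 4.1 | 0.75 | 1.58 |
| LDL 4.9 | 0.89 | 1.88 |

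Each trigger falls to 2.6 / 5.5 = 47% of the intended level. Total cholesterol from 1.13 to 2.00 g/L, inside the ATP III desirable band, would be flagged. So would LDL from 0.75 to 1.00 g/L, inside the optimal band.

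**4. Hemoglobin.** One litre is 10 dL, so g/L = 10 × g/dL. With 0.1:

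- The SAP's normal values of 12 to 17 g/dL become 1.2 to 1.7 g/L, so every patient is below 95 and 115 g/L. Escaping the low flag would need more than 95 / 0.1 = 950 g/dL (women) or 115 / 0.1 = 1150 g/dL (men).
- The high limits would need 165 / 0.1 = 1650 and 185 / 0.1 = 1850 g/dL.
- The 20 g/L fall would need 20 / 0.1 = 200 g/dL. With the correct factor it is 20 / 10 = 2 g/dL.

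**5. Erythrocytes.** ×10¹²/L = 0.001 × (×10⁹/L). The SAP's normal values of 4.2 to 6.2 millions/mm³ are 4200 to 6200 ×10⁹/L. Multiplied by 1000 they read 4.2 to 6.2 million, against a limit of 6. The limit would trigger at 6 / 1000 = 0.006 ×10⁹/L instead of 6 / 0.001 = 6000 ×10⁹/L. If the data are in fact stored as 4.2 and the factor is still applied, 4.2 × 1000 = 4200, which is also flagged.

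**The case against.** The factors themselves cannot be defended. The case on the other side concerns reach and weight.

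- **The link to Appendix J is inferred.** No sentence says that item (19) feeds the PCSA limits, and its hematology lines name no analyte. This stands as a gap in the text. But the source units match SAP 5.1.4 for lipids and erythrocytes, and E 20 and the norms for hemoglobin. The target units match Appendix J, and the SAP offers no other route.
- **Erythrocytes depend on the units actually held.** Tests are local, and the norms in millions/mm³ are numerically already on the ×10¹²/L scale. If data are stored that way and left unconverted, the row would be right. That is true, but it means not following the printed rule.
- **Review might catch it.** SAP 8.3 calls for outputs to be checked for nonsensical values. Any total cholesterol above 9.1 / 5.5 = 1.65 g/L would read above the study's own exclusion limit. A row at 100% should stand out, and the lipid shift might too, although it is less conspicuous. A possible catch does not make the formula right.
- **2.6 comes from rounded limits.** Allowing for rounding to one decimal, E 20 permits 9.05 / 3.50 = 2.586 to 9.15 / 3.50 = 2.614. The LDL limit of 4.1 permits 4.05 / 1.60 = 2.531 to 4.15 / 1.60 = 2.594. The overlap lies just below 2.6, a difference of about 0.5%. E 20 also gives no pair for LDL or HDL. Both points are fair but small beside a factor that is 2.1 times too high.
- **The outputs are descriptive.** The study is single-arm and plans no test of these percentages. That limits the damage but leaves a planned safety result wrong.

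**Conclusion.** The concern holds. All three conversions are wrong as printed: the lipid factor by the documents' own pairs, the hematology factors by unit arithmetic. Nothing elsewhere in the documents corrects them.

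If they are programmed as written, four PCSA rows are misstated. The total cholesterol and LDL triggers fall to 47% of the intended level. How many extra patients that flags cannot be derived from the documents. The low-hemoglobin and erythrocyte rows go to 100%, and the high-hemoglobin and hemoglobin-fall criteria become impossible to meet.

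This rests on four assumptions: the printed formulas are the ones programmed; they feed Appendix J; hemoglobin is held in g/dL and erythrocytes are converted as printed; and the cholesterol factor also applies to LDL, which the ATP III match supports.

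The triglyceride row is undetermined because its limit is not legible in the text available, and no HDL limit is shown. The remaining PCSA rows, the dose-modification rules and the primary RAID analysis are unaffected. The point must be fixed, because following the plan gives wrong safety figures.

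**What to change.** Replace item (19) with one line per analyte:

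- total, HDL and LDL cholesterol: mmol/L = 2.6 × g/L (the E 20 cholesterol pair, extended to HDL and LDL), or a more exact factor with its source
- triglycerides: mmol/L = 1.12 × g/L (the E 20 pair)
- hemoglobin: g/L = 10 × g/dL
- erythrocytes: ×10¹²/L = 0.001 × (×10⁹/L)

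In SAP 5.1.4, correct the unit labels of white blood cells (printed in g/dL) and hemoglobin (printed in ×10⁹/L), which appear to be swapped, and confirm the units actually collected for every converted test. State that these conversions feed Appendix J. Reconcile the g/L units for lipids in SAP 5.1.4 with protocol 9.2.2.2, which calls for international units in all tables.

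If outputs already exist, check which constants were used and regenerate the four rows if they were the printed ones. Check the triglyceride row in the same way. The cost is SAP wording and a few program constants; no new data are needed.

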APPENDIX B: DECISION TABLES

To evaluate the variation of each total score of the PROs in classes, decision tables below will be used.

Total RAID score		At Vx	
		Acceptable status	Non acceptable status
At baseline	Acceptable status	Unchanged (Acceptable status)	Worsening
	Non acceptable status	Improvement	Unchanged (Non acceptable status)

Figure 3: Decision table for the variation of the total RAID score in classes

HADS scores		At Vx		
		Normal	Borderline Abnormal	Abnormal
At baseline	Normal	Unchanged (Normal)	Worsening	Worsening
	Borderline Abnormal	Improvement	Unchanged (Borderline Abnormal)	Worsening
	Abnormal	Improvement	Improvement	Unchanged (Abnormal)

Figure 4: Decision table for the variation of the HADS scores (anxiety and depression) in classes

HAQ-DI scores		At Vx			
		Without any difficulty	With some difficulty	With much difficulty	Unable to do
At baseline	Without any difficulty	Unchanged (Without any difficulty)	Worsening	Worsening	Worsening
	With some difficulty	Improvement	Unchanged (With some difficulty)	Worsening	Worsening
	With much difficulty	Improvement	Improvement	Unchanged (With much difficulty)	Worsening
	Unable to do	Improvement	Improvement	Improvement	Unchanged (Unable to do)

Figure 5: Decision table for the variation of the HAQ-DI domain scores in classes

IPAQ total score		At Vx		
		Low physical activity	Moderate physical activity	High physical activity
At baseline	Low physical activity	Unchanged (Low physical activity)	Improvement	Improvement
	Moderate physical activity	Worsening	Unchanged (Moderate physical activity)	Improvement
	High physical activity	Worsening	Worsening	Unchanged (High physical activity)

Figure 6: Decision table for the variation of the IPAQ classification in classes

Comparison	Classes
Value at Vx < Value at baseline	Decrease
Value at baseline = Value at Vx	Unchanged
Value at baseline < Value at Vx	Increase

Figure 7: Decision table for the size of the rheumatoid nodule evolution in classes

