## 11 STATISTICAL CONSIDERATIONS

### 11.1 DETERMINATION OF SAMPLE SIZE

The primary study objective is to assess the change in RAID score from baseline to W24. A sufficient precision (half-length of the 95% confidence interval) is required. According to the literature (44, 45, 46) and findings from the MONARCH and TARGET studies (22, 33), the standard deviation (SD) of the RAID score could be estimated at 2.5 points. On this basis, a sample size of 140 patients (122 evaluable, if 20% non-evaluable patients) produces a precision, two-sided 95% confidence interval (CI), with a distance from the mean to the limits that will be less than 0.5 when the estimated SD is 2.5. Table below gives the 95% CI of change from baseline to W24 of RAID score with this precision (0.44), assuming that the change from baseline will be from 30% to 50% (MCII defined by Dougados in 2012; 47) of baseline score.

Expected change from baseline to W24 of RAID score (Relative to baseline %)	RAID score at Baseline	Expected change from baseline to W24 of RAID score (Absolute value)	95% CI (precision =0.5)
30%	65	2,0	[1,5 ; 2,5]
	5	1,5	[1,0 ; 2,0]
	3,5	1,1	[0,6 ; 1,6]
50%	6,5	3,3	[2,8 ; 3,8]
	5	2,5	[2,0 ; 3,0]
	3,5	1,8	[1,3 ; 2,3]

*Note that on MONARCH study (22), the % of change from baseline was 49.6% (3.32/6/69) and in TARGET study (33) 47.4% (3.24/6.83).*

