5.1.3. Secondary endpoints (6-month core period)

- **PROs questionnaires**

- [RAID](#) score per item and total score^{DD}
The RAID score gives a number between 0 and 10. A higher score on the RAID indicates more impact of the disease.
A score ≤ 2 out of 10 is considered a patient-acceptable status.

- Hospital Anxiety and Depression Scale ([HADS](#)):
 - Per item
 - Anxiety calculated score as quantitative^{DD} and in classes
 - Normal (0-7)
 - Borderline abnormal (8-10)
 - Abnormal (11-21)
 - Depression calculated score as quantitative^{DD} and in classes:
 - Normal (0-7)
 - Borderline abnormal (8-10)
 - Abnormal (11-21)
- Multidimensional Assessment of Thymic States ([MATHys](#))^{DD}
 - Per item
 - 5-dimension scores:
 - Emotion
 - Cognition
 - Psychomotor function
 - Motivation
 - Sensory perception
 - MATHys total score
- Functional Assessment of Chronic Illness Therapy – Fatigue ([FACIT-F](#)) per item and total score
- Health Assessment Questionnaire - Disability Index ([HAQ-DI](#)) per domain (dressing & grooming, arising, eating, walking, hygiene, reach, grip and activities) and total score.
- International Physical Activity Questionnaire ([IPAQ](#)) classification per domain and total score as quantitative and in classes:
 - Low physical activity
 - Moderate physical activity
 - High physical activity
- Patient global assessment of disease activity using a 100 mm Visual Analogue Scale (VAS)
- Duration of morning stiffness (minutes)
- **Evaluation of RA activity**
- Erythrocyte sedimentation rate (ESR) (1st hour) (mm/h)
- Number of swollen joints (SJC)
- Number of tender joints (TJC)
- DAS28-ESR^{DD}
 - Low Disease Activity (LDA) (Yes/No)
 - Remission (Yes/No)
- CDAI^{DD}
 - Low Disease Activity (LDA) (Yes/No)
 - Remission (Yes/No)

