5.3.2.2. Primary efficacy analysis

The primary study objective is to describe the effect of sarilumab on the variation of the total [RAID](#) score from baseline to V5 (W24). Mean change from baseline (V2) of the total [RAID](#) score to W24 (V5) will be provided with its bilateral 95% CI.

Change from baseline in total [RAID](#) score after 24 weeks will be provided using a mixed model repeated measurement. This model includes total [RAID](#) score at baseline as covariate, and interactions between the covariate and visit.

SAS code:

```
Proc MIXED;  
Class Visit;  
Model RAID_score_change= Visit + Raid_score_baseline*Visit;  
Repeated Visit / type=UN sub=id;  
Run;
```

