5.3.2.3. Secondary efficacy analyses

For each of the secondary endpoints, values at each assessment visit over the treatment period and changes from baseline for each PROs questionnaires total score to evaluate the RA activity will be presented (absolute and relative variation). 95% CI will be provided.

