APPENDIX A: DERIVED DATA

The derived data are variables which are calculated from the raw data in the CRF/eCRF and not included in the database (e.g.: AUC, total score, duration, summary value from repeated observations, study exposure, study drug exposure, study drug cumulative dose, etc.).

The formula used for derived data should be provided and examples may be necessary to clarify the calculation. The strategy for missing data must be specified in the calculation of derived data (e.g.: the minimum number of observations required to calculate an average score, handling incomplete dates).

All references used to calculate the derived data should be mentioned below.

The following derived data will be calculated and included in the listings:

(1) SUBGROUPS DECISION

Treatment started before screening visit and ongoing at screening visit	Prescribed treatment at baseline
csDMARDs	Sarilumab + csDMARDs
Biological therapy	Sarilumab + csDMARDs
csDMARDs or biological therapy	Sarilumab in monotherapy

(2) DAS28-ESR

$DAS28-ESR = 0.56 \times \sqrt{TJC28} + 0.28 \times \sqrt{SJC28} + \ln(ESR) + 0.014 \times PtGA$ (in mm)

Where:

- ln is the natural logarithm
- SJC is the swollen joints
- TJC is the tender joints
- PtGA is the patient's global assessment of disease activity (using a 100 mm VAS)
- ESR is the erythrocyte sedimentation rate (mm/h)

(3) CDAI

$CDAI = TJC28 + SJC28 + PtGA(\text{in cm}) + PhGA(\text{in cm})$

Where:

- SJC is the swollen joints
- TJC is the tender joints
- PhGA is the physician's global assessment of disease activity (using a 100 mm VAS)
- PtGA is the patient's global assessment of disease activity (using a 100 mm VAS)

(4) BMI

BMI (kg/m²) will be derived as $\text{Weight (kg)} / [\text{Height (cm)} / 100]^2$ and rounded to the nearest decimal.

(5) Time between baseline and initial diagnosis (years)

Time between baseline and initial diagnosis in years will be calculated as $(\text{initial diagnosis date} - \text{baseline visit date} + 1) / 365.25$.

(6) Changes from baseline (V2)

Absolute variation (points) from baseline will be calculated as a difference from baseline (e.g. assessment at the visit – assessment at baseline).

Relative variation (%) from baseline will be calculated as: $((\text{assessment at the visit} - \text{assessment at baseline}) / \text{assessment at baseline}) * 100$.

If necessary, evolution will be presented according to decision tables from Appendix B.

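### The SAP's only categorical rule for RAID change moves only when the score crosses 2, so many patients with a large reduction would be labelled unchanged

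*SAP*

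**What the plan says.** SAP section 5.1.3 sets the class boundary: "A score ≤ 2 out of 10 is considered a patient-acceptable status". Appendix B introduces its tables with "To evaluate the variation of each total score of the PROs in classes, decision tables below will be used". Figure 3 is the RAID table. It crosses two states at baseline with the same two states at a later visit. Moving from above 2 to 2 or below is called improvement, and the reverse is called worsening. Both diagonal cells are called unchanged; the one for patients above 2 at both times reads "Unchanged (Non acceptable status").

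Appendix A, item 6, makes use of the tables conditional: "If necessary, evolution will be presented according to decision tables from Appendix B". It does not say when they become necessary.

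The rest of the RAID reporting is continuous. The primary analysis (SAP 5.3.2.2) gives a mean change "to W24 (V5) will be provided with its bilateral 95% CI", together with a repeated-measures mixed model. For the secondary analyses (SAP 5.3.2.3), changes in each "questionnaires total score to evaluate the RA activity will be presented (absolute and relative variation").

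Protocol section 11.1 uses a different yardstick for improvement. It plans the sample size "assuming that the change from baseline will be from 30% to 50" per cent of the baseline score and labels this the MCII. That yardstick is not carried into any RAID endpoint or table in either document.

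**The concern.** Figure 3 takes a cut-off for being in an acceptable state and attaches words of change to it. A fall from 9.0 to 2.5 and a rise from 2.1 to 10 are both unchanged, while a move from 2.0 to 2.1 is a worsening. These results follow from the rule as written and need no assumption.

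The stated primary objective is to describe how patients' perception evolves, measured by RAID. If Figure 3 is produced, it will be the only RAID table that uses the words improvement and worsening. It would put many patients who meet the protocol's own 30-50% yardstick in the unchanged row. It also gives no share of patients who reached that yardstick, and its worsening row depends heavily on how many patients happen to start at or below 2.

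**Working it through.** **Inputs from the documents.** Cut-off 2 (SAP 5.1.3); the Figure 3 rule (SAP Appendix B); planning baselines, planned falls and an SD of 2.5 (Protocol 11.1). One baseline in that table is printed as 65; it is read as 6.5, because 30% of 6.5 is 1.95, which matches the 2.0 shown. Protocol 11.1 also reports two earlier trials: "the % of change from baseline was 49.6% (3.32/6/69) and in TARGET study (33) 47.4% (3.24/6.83").

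**Plan's own figures.** 3.32/6.69 = 49.6% and 3.24/6.83 = 47.4%. Both reproduce, reading the first denominator as 6.69.

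**Step 1: apply Figure 3 to the protocol's planning rows.**

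| Baseline | Planned fall | Week 24 | Figure 3 class |
|---|---|---|---|
| 6.5 | 2.0 (30%) | 4.5 | unchanged |
| 5 | 1.5 (30%) | 3.5 | unchanged |
| 3.5 | 1.1 (30%) | 2.4 | unchanged |
| 6.5 (bold row) | 3.3 (50%) | 3.2 | unchanged |
| 5 | 2.5 (50%) | 2.5 | unchanged |
| 3.5 | 1.8 (50%) | 1.7 | improvement |

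Five of six rows are unchanged. So are both earlier-trial means: 6.69 - 3.32 = 3.37 and 6.83 - 3.24 = 3.59.

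**Step 2: fall needed to be classed as improved.** This is 1 - 2/baseline: 69% from 6.5, 70% from 6.69, 71% from 6.83 and 60% from 5. Any baseline above 4 with exactly a 50% fall stays unchanged.

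**Step 3: share of patients affected.** Assumptions not in the documents: normal baseline with mean 6.7 and SD 1.5-2.5; normal change with mean -3.3 and SD 2.0-2.5; correlation of change with baseline -0.4; scores limited to 0-10. One million simulated patients per scenario.

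| Baseline SD / change SD | Unchanged | Of these, fall of 30% or more | Of these, fall of 50% or more | Of all with a fall of 50% or more, labelled unchanged | Any rise | Labelled worsening |
|---|---|---|---|---|---|---|
| 1.5 / 2.0 | 76.3% | 67.9% | 33.3% | 51.9% | 5.0% | 0.02% |
| 1.5 / 2.5 | 72.5% | 59.8% | 30.1% | 44.4% | 9.4% | 0.04% |
| 2.0 / 2.0 | 74.3% | 68.0% | 32.9% | 49.5% | 4.9% | 0.15% |
| 2.0 / 2.5 | 71.3% | 60.0% | 30.2% | 43.5% | 9.3% | 0.27% |
| 2.5 / 2.0 | 73.4% | 68.0% | 33.1% | 48.8% | 4.9% | 0.31% |
| 2.5 / 2.5 | 70.7% | 60.6% | 31.1% | 44.0% | 9.2% | 0.62% |

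A second model serves as a check: beta-shaped scores, SD 2.0-2.5, correlation 0.3-0.5 between baseline and Week 24, baselines 6.5-6.83 with a mean fall of 47-50%. It labels 36-48% of patients with at least a 50% fall as unchanged. About 50-55% of its patients have such a fall, against 27-36% classed as improved by Figure 3.

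**Step 4: who can be labelled worse.** Only a patient starting at or below 2. The share is P(baseline ≤ 2), for example Φ((2 - 6.5)/2.5) = Φ(-1.8) = 3.6% for a normal baseline with mean 6.5 and SD 2.5. Over SD 1.5-2.5 and normal, truncated-normal and beta shapes:

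| Mean baseline | Start at or below 2 | Of 140 patients |
|---|---|---|
| 6.5-6.83 | about 0.1-6% | 0-8 |
| 5 | about 2-14% | 3-20 |
| 3.5 | about 15-35% | 21-49 |

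Under the Step 3 model with a mean fall of 30-50%, the share actually labelled worsening is 0.6-4.1% at mean 5 and 3.9-9.0% at mean 3.5.

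**The case against.** Four objections carry weight.

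- **The table may never be produced.** Appendix A makes it conditional. That stands, and it limits the consequence. But no trigger is given, Appendix B itself says without condition that the tables will be used, and if the table is made this is its rule.
- **Continuous results are reported in full.** This also stands. SAP 3.1 requires median, interquartile range, minimum and maximum, so quartiles of relative change show roughly how many patients passed a given reduction, and the maximum shows the worst rise. A reader might infer that the plan hides most improvement and nearly all deterioration; the documents do not support that. What is missing is the exact proportion at the protocol's own thresholds.
- **It is openly a table of classes.** The cell names the state in brackets, and the HADS and IPAQ tables follow the same convention. This is fair, but RAID has only two classes, so a very wide range of change falls within one cell.
- **No RAID responder endpoint was ever defined.** This is correct. The 30-50% range appears only in the sample-size reasoning, so the threshold proportions would be additions. They should be presented as descriptive, which is how Protocol 11.4.2.3 treats all analyses.

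A reader might also infer that worsening cannot occur under the rule. The documents do not support that either: entry is by DAS28-ESR, no criterion sets a minimum RAID, and Protocol 11.1 plans for mean baselines of 5 and 3.5 as well as 6.5. The 5-9% with any rise in Step 3 should not be read as clinically important deterioration, because it counts rises of any size. Under the same assumptions only about 1-3% rise by 30% or more.

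**Conclusion.** The point holds in a limited form. Figure 3 labels RAID change only when the score crosses 2, and a study that performed exactly as planned in the bold row would see its average patient classed as unchanged. That part rests on the documents alone.

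The size rests on assumptions about spread, correlation and shape: about 71-76% unchanged, and about 43-52% of patients with at least a 50% fall among them. A different model gives 36-48% for the latter, so the direction does not depend on one choice. The low count of worsening is conditional on a baseline near 6.5-6.8.

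No estimate or conclusion of the primary analysis changes. The defect is a misleading label in one conditional secondary table, worth correcting because the correction is cheap.

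**What to change.** 1. Rename the four cells of Figure 3 as status transitions: reached, kept, lost, or not in acceptable status. Keep the cut-off of 2 for that purpose.
2. From the relative variation already derived in Appendix A, item 6, add the proportions of patients with at least 30% and at least 50% reduction (the range that Protocol 11.1 cites as the MCII), with any increase, and with at least 30% increase. Give them at W4, W12 and W24 with 95% CI, as descriptive results. Relative variation is undefined at a baseline of 0, so state how such a patient is counted.
3. Reserve the words improvement and worsening for these change-based proportions.
4. State in Appendix A when the Appendix B tables will be produced.

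The cost is SAP wording and one extra table from data already collected and derived. The primary analysis is unchanged. The downside is a few more descriptive proportions.
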